### 1.1 Endpoints in Sarcoma Studies

Historical data show that the prognosis for advanced sarcoma patients who have failed at least one prior therapy is poor, with 90% experiencing disease progression within 6 months (i.e., the 6-month progression-free survival is 10%).[7] Thus, we consider the prolonged progression-free survival in this patient population to be a meaningful result.

Progression-free survival (PFS) is used increasingly as a metric for comparison of chemotherapeutic agents in sarcomas, given that response rates are relatively low, at least in part due to the biology of chemotherapy responses of sarcomas, which die more frequently by senescence than by apoptosis. The best available data regarding PFS comes from EORTC databases.[7] In this analysis, PFS was estimated in both previously treated and previously untreated patients, based on analysis of 12 clinical trials of different agents in which in only two cases (ifosfamide and dacarbazine) was there a significant response rate. Comparison was made between responses to these two agents vs. inactive agents (all others examined in these studies). Response assessment was made by WHO criteria for these studies performed reported between 1991 and 1999. A total of 1154 patients were examined who had not received prior therapy, while 146 cases with prior anthracyclines who then received ifosfamide or dacarbazine constituted the responding cohort. 234 patients receiving what were termed inactive agents/regimens were used as a comparator.[7] For patients who had received prior therapy, PFS was better with active drugs than inactive drugs in a multivariate analysis. Performance status was of borderline significance ( $p=0.08$ ). For previously treated patients, PFS was 21% at 3 months for inactive drugs/regimens, and 39% for active drugs; 6 month PFS was 8% with inactive regimens, and 14% for active regimens. In patients who had not received prior chemotherapy, 3 month PFS varied from 44-77%, depending on histology, and 6 month PFS varied between 30% and 56%.

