## 1.9 Rationale for cohort expansion in GIST

GIST are the most common sarcomas of the digestive tract and are thought to arise from or share a common ancestor with the interstitial cells of Cajal, the autonomic pacemaker cells of the gut that coordinate peristalsis. Approximately 4000 to 6000 new cases of GIST are diagnosed in the US each year. Between 75% and 80% of these tumors contain activating mutations of KIT or PDGFR-alpha, providing oncogenic signaling and driving tumor growth. Given this, multiple small molecule tyrosine kinase inhibitors (TKI) against KIT and PDGFRA, such as imatinib, sunitinib, sorafenib and dasatinib, have been evaluated for the treatment of this disease.

Advanced GIST is refractory to conventional chemotherapy or radiotherapy, but multiple TKIs have been shown to have antitumor activity in this disease. Imatinib mesylate, a multi-targeted TKI with activity against PDGFR, KIT, BCR-ABL, ABL and LCK, has become the first line standard of care in advanced GIST achieving disease control in 70% to 85% of patients, with a median progression free survival of 20 to 24 months. Although treatment with imatinib has greatly increased survival and quality of life for patients with advanced GIST, a subset of patients acquire kinase mutations in KIT or PDGFR-alpha that interfere with imatinib activity and ultimately lead to imatinib resistance.

At time of progression, the currently accepted treatment strategies include dose escalation of imatinib or transition to treatment with sunitinib. Sunitinib is a multi-targeted TKI with a kinase spectrum including VEGF as well as PDGFR and KIT, among others. In an international phase III trial of imatinib refractory patients, sunitinib showed a median time to tumor progression of 27.3 weeks compared to 6.4 weeks in those on placebo. Based on this and other data, sunitinib has been FDA approved for the treatment of imatinib-refractory or intolerant advanced GIST.

Although treatment of GIST with tyrosine kinase inhibitors results in demonstrated clinical benefit, this efficacy is not indefinite and treatment with KIT inhibition does not result in the cure of patients with advanced disease. Alternate options are necessary to improve outcomes for patients with TKI resistant GIST.

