- C Every 6 weeks for 12 weeks, then every 8 weeks until evidence of progression or relapse. Scans may be performed +/- 7 days from scheduled date. During the first 12 weeks of therapy, patients can be considered for continuation of treatment (see [Section 7.1](#) for further details and footnote D below). Confirmatory scans to be obtained at least 4 weeks following documentation of objective response (see [Section 11.0](#)). Response assessment should include assessment of all sites of disease and use the same imaging method as was used at baseline. For patients receiving initial treatment beyond 2 years from randomization date; scans may be performed every 3 months for year 3, every 4 months for year 4, every 6 months for year 5 and then yearly thereafter. One confirmatory scan continues to be required if patient achieves a response for the first time and during this period. Thereafter, returning to the assessment schedule.
- D If there is evidence of progression in the first 12 weeks, treatment is allowed to be continued. The patient's baseline assessment is now the 1st assessment showing progression (not the pre-study disease assessment) and is used for the remainder of the patient's initial treatment assignment (not crossover). Contact the Data Manager or Study Chair for questions. If this occurs, an additional scan is to be scheduled 4 weeks from the regular scan (i.e. at week 10 or 16). Thereafter, the patient will have a scan every 8 weeks. See also [section 7.1](#) for further information.
- E. **Crossover Patients Only:** For patients who crossover to dual agent therapy, a baseline scan is required  $< 28$  days prior to re-registration. After initiation of dual agent therapy scans are every 6 weeks for 12 weeks, then every 8 weeks until evidence of progression or relapse (scans may be done +/- 7 days from due date). During the first 12 weeks of therapy, patients can be considered for continuation of treatment (see [Section 7.1](#) for further details and footnote D above with the appropriate reset for baseline disease measurement. Contact the Data Manager or Study Chair for questions). Confirmatory scans are to be obtained at least 4 weeks following documentation of objective response (see [Section 11.0](#)). Response assessment should include assessment of all sites of disease and use the same imaging method as was used at the baseline measurements associated with crossover. For patients receiving crossover

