### 11.3.3 Measurement at Follow-up Evaluation:

**Important: Refer to [Section 11.1](#) for a full description of the correct baseline scan to use due to the retreatment after PD during treatment in the 1st 12 weeks, as well as baseline scan to be used for crossover treatment.**

- A subsequent scan must be obtained at least 4 weeks following initial documentation of an objective status of either complete response (CR) or partial response (PR). This is applicable to both response during initial treatment assignment and to response to crossover to dual agent therapy.
- In the case of stable disease (SD), follow-up measurements must have met the SD criteria at least once after study entry at a minimum interval of 6 weeks (see [Section 11.4.4](#)).
- If a scan shows progressive disease during the first 12 weeks of therapy and patient and treating physician elect to remain on treatment, imaging should be repeated within 4 weeks. If that imaging confirms progression, then that patient has progressive disease and therapy should be discontinued. See [Section 7.1](#) for further details.
- The cytological confirmation of the neoplastic origin of any effusion that appears or worsens during treatment when the measurable tumor has met criteria for response or stable disease is mandatory to differentiate between response or stable disease (an effusion may be a side effect of the treatment) and progressive disease.
- Cytologic and histologic techniques can be used to differentiate between PR and CR in rare cases (e.g., residual lesions in tumor types such as germ cell tumors, where known residual benign tumors can remain.)

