#### 11.4.3.2 Evaluation of Target Lesions

**Important: Refer to [Section 11.1](#) for a full description of the correct baseline scan to use due to the retreatment after PD during treatment in the 1st 12 weeks, as well as baseline scan to be used for crossover treatment.**

- **Complete Response (CR):** All of the following must be true:
  - a. Disappearance of all target lesions.
  - b. Each target lymph node must have reduction in short axis to < 1.0 cm.
- **Partial Response (PR):** At least a 30% decrease in PBSD (sum of the longest diameter for all target lesions plus the sum of the short axis of all the target lymph nodes at current evaluation) taking as reference the BSD (see [Section 11.4.1](#)).
- **Progression (PD):** At least one of the following must be true:
  - a. At least one new malignant lesion, which also includes any lymph node that was normal at baseline (< 1.0 cm short axis) and increased to  $\geq$  1.0 cm short axis during follow-up.
  - b. At least a 20% increase in PBSD (sum of the longest diameter for all target lesions plus the sum of the short axis of all the target lymph nodes at current evaluation) taking as reference the MSD ([Section 11.4.1](#)). In addition, the PBSD must also demonstrate an absolute increase of at least 0.5 cm from the MSD.
  - c. See [Section 11.3.2](#) for details in regards to the requirements for PD via FDG-PET imaging.
- **Stable Disease (SD):** Neither sufficient shrinkage to qualify for PR, nor sufficient increase to qualify for PD taking as reference the MSD.

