## 13.4 Secondary Endpoints

- Evaluating adverse event rates (NCI CTCAE v4.0), within each study treatment arm. Categorical data analysis will be used to summarize adverse event rates and as a maximum severity during treatment for each patient and AE classification.
- Evaluating duration of response, clinical benefit rate (CBR), progression-free survival (PFS), and overall survival (OS), within each study treatment arm. Patients having PD within the first 12 weeks of starting treatment which is not a PD at their 4 week confirmation assessment will not be classified as having PD for time to event analyses. That is, estimates for response, CBR, and PD endpoints will not be censored at the first PD in such cases. Patients who are unable to continue treatment for a 4-week confirmation of PD occurring within the first 12 weeks of treatment will be counted as having PD at their first date of PD during the treatment period (eg, initial, crossover). In addition, disease assessment data beyond the date of crossover will not be included in the evaluation of the primary endpoint and for those patients crossing to dual agent treatment from single agent treatment. Such patients will be censored for estimating

duration of response, CBR, and PFS. Patients will be additionally censored at their most recent disease assessment prior to receiving any anti-cancer therapy after ending study treatment.

Kaplan-Meier methodology will be used to evaluate time to event endpoints: duration of response (time from first response to disease progression), PFS (time from randomization to the earliest of either disease progression or death from any cause), and OS (time from randomization to death from any cause). The CBR will be evaluated by counting up the number of patients with a response or stable disease (PR, CR, SD) and dividing by the total number of evaluable patients. Cumulative Incidence Function methodology may be used, as appropriate.

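### The clinical benefit rate counts any stable disease from about week 6, so roughly 40-50% of patients could count with no drug effect

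*Combined protocol and SAP*

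**What the plan says.** Section 13.4 (Secondary Endpoints) gives the definition: "The CBR will be evaluated by counting up the number of patients with a response or stable disease (PR, CR, SD"), over the number of evaluable patients. It states no duration, landmark time or confirmation for SD.

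The only duration rule for SD is in Section 11.3.3: "follow-up measurements must have met the SD criteria at least once after study entry at a minimum interval of 6 weeks". Section 11.4.3.2 defines SD for target lesions by exclusion: "Neither sufficient shrinkage to qualify for PR, nor sufficient increase to qualify for PD taking as reference the MSD". Section 5.0, footnote C, sets the scans: "Every 6 weeks for 12 weeks, then every 8 weeks until evidence of progression or relapse", with the allowance "Scans may be performed +/- 7 days from scheduled date". The first on-treatment scan is therefore at about week 6, and a single non-progressing result there makes the patient a clinical benefit case.

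Section 13.4 also sets aside a progression (PD) in the first 12 weeks that is not PD at the 4-week repeat scan, and it speaks of censoring crossover patients for CBR. Section 13.5 lists clinical benefit among the outcomes for the biomarker models. No section gives an expected, null or reference CBR.

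**The concern.** Under this definition a patient who is SD at week 6 and progresses at week 12 scores the same as a patient with a lasting complete response. Section 1.1 says of this population: "we consider the prolonged progression-free survival in this patient population to be a meaningful result". A one-scan SD count does not measure that.

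Sections 13.1 and 13.5 exclude comparison between the arms, and there is no control. Each of the eight treatment-by-cohort groups will report a CBR with nothing beside it. In fast-progressing disease a sizeable fraction of patients has not yet progressed at six weeks on an inactive regimen. Their share is the level that a reader needs in order to interpret the result, and the plan does not supply it. The same binary variable then enters the exploratory models of Section 13.5.

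**Working it through.** The plan states no CBR figure, so there is none to reproduce. The check asks what CBR would be expected with no drug effect, taking it as the proportion progression-free at the qualifying scan.

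**Inputs**
- Previously treated sarcoma, Section 1.1: "PFS was 21% at 3 months for inactive drugs/regimens, and 39% for active drugs; 6 month PFS was 8% with inactive regimens". These data used WHO criteria.
- The same section gives an overall 6-month PFS of 10% (sensitivity only), and 39% at 3 months and 14% at 6 months for active drugs.
- Imatinib-refractory GIST, Section 1.9: "sunitinib showed a median time to tumor progression of 27.3 weeks compared to 6.4 weeks in those on placebo".
- Scans at weeks 6, 12 and 20, each +/- 7 days. Three months is taken as 13.04 weeks and six months as 26.09.

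**Formulas**
- Weibull through both inactive-drug points: k = ln(ln 0.08 / ln 0.21) / ln 2 = 0.695; S(t) = exp[ln 0.21 × (t/13.04)^0.695].
- Exponential through the 3-month point: S(t) = 0.21^(t/13.04).
- GIST placebo, exponential assumed: S(t) = 0.5^(t/6.4).

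**Progression-free with no drug effect**

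| Curve | Week 5 | Week 6 | Week 7 | Week 12 | Week 20 |
|---|---|---|---|---|---|
| Inactive drugs, Weibull | 45% | 40% | 36% | 23% | 12% |
| Inactive drugs, exponential | 55% | 49% | 43% | 24% | 9% |
| GIST placebo, exponential | 58% | 52% | 47% | 27% | 11% |

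**Sensitivity**
- Log-normal and log-logistic curves through the same two inactive-drug points give 45% and 48% at week 6.
- One-point exponentials from six months give 0.08^(6/26.09) = 56% and 0.10^(6/26.09) = 59% at week 6. The first fits poorly: it implies 0.08^0.5 = 28% at 3 months, against the stated 21%. At week 20 these two curves give 14% and 17%.
- The exponential from 3 months implies 0.21² = 4.4% at 6 months, against the stated 8%, so the two-point curves suit the inactive-drug data better.
- The range of 36-59% runs from the Weibull at week 7 to the 10% exponential at week 6. It leaves out the one-point six-month curves at week 5 (62% and 64%). A scan before day 42 would not strictly meet the six-week minimum in any case.

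**What this means per arm**
- In expected counts: 38 × 0.40 to 0.49 = 15-19 patients; 12 × 0.40 to 0.49 = 5-6; 24 × 0.52 = 12-13.
- By the binomial, an arm of 12 with no drug effect shows a CBR of at least 50% with probability 34% (Weibull) to 58% (exponential). A GIST arm of 24 does so with probability 66%.
- On the Weibull curve, 1 − 0.229/0.403 = 43% of those SD at week 6 have progressed by week 12.

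**Active against inactive drugs**
A Weibull through 39% and 14% gives 66% at week 6 and 23% at week 20. The ratio to inactive drugs is 66/40 = 1.6 at week 6 and 23/12 = 1.9 at week 20. The absolute gap narrows, from 26 to about 10 points. What the later landmark mainly buys is a low no-effect level.

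**The case against.** The strongest reply is that this is a choice of definition and not a mistake. Counting CR, PR and SD is a recognised convention, and Section 1.4 describes the earlier ipilimumab study in synovial sarcoma in the same terms. No section calls for a longer SD duration. Section 2.2.2 lists PFS, duration of response and OS beside CBR, and these separate brief stability from lasting benefit. Every go/no-go rule in Section 13.3 uses confirmed response, and Section 13.5 is openly exploratory. All of this stands, and it limits the point to how one descriptive endpoint is read.

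Two stronger readings are tempting. A reader might take 40-52% as the protocol's own figure. It is not: no six-week rate appears anywhere. The sarcoma inputs used WHO criteria while the trial uses RECIST 1.1. The untreated figure is one time-to-progression median, in GIST only, and it falls inside the first-scan window. The pooled history is also applied to cohorts with a different histology mix. A reader might also infer that most benefit cases in the biomarker models would be slow natural growth. That depends on the unknown drug effect and is not shown.

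A landmark version has its own difficulties. Patients who stop for toxicity may be scanned less often, because a Section 5.0 footnote sets six-monthly follow-up while footnote C continues 8-weekly scans. Crossover and reset-baseline patients need explicit rules. These difficulties shape the fix but do not remove the need for it: a later progression-free scan can still qualify a patient who stopped early.

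**Conclusion.** The point holds as a limit on interpretation. Sections 13.4, 11.3.3 and 5.0 together let one non-progressing scan at about week 6 count as clinical benefit. In uncontrolled arms such a rate separates an inactive regimen from a beneficial one poorly. By extrapolation the no-effect level is roughly 40-50%, or about 36-59% over the curves and scan window considered, against about 9-12% at week 20 on the main curves.

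This rests on the assumed curve shapes, on historical PFS or time to progression standing in for the proportion without PD at the scan, and on those populations resembling the cohorts. The range leaves out patients whose early PD is set aside after the baseline reset of Section 7.1, who could push the rate up.

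A reader might conclude that an inactive arm could be declared promising. The documents do not support that, because no decision rule uses CBR. The change is a cheap improvement to a secondary endpoint and to the clinical benefit outcome in Section 13.5.

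**What to change.** In Section 13.4 add a durable CBR: confirmed CR or PR, or SD with no PD (as PD is counted in that section) through at least one evaluable scan 17 weeks or more after randomization, the same origin as PFS. On the existing calendar this is normally the week-20 scan, or the week-18 or week-24 scan under footnote D. The 17-week floor allows for the 7-day window (18 − 1 = 17). Even with the 14 days allowed between registration and treatment, a week-12 scan falls no later than week 12 + 1 + 2 = 15 and cannot qualify.

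State these cases:
- Patients who stopped early for toxicity qualify on a later progression-free scan.
- Patients who cross over or start other anti-cancer therapy before a qualifying scan count as no benefit. This replaces censoring, which has no meaning for a simple proportion.
- Patients on a reset baseline are identified, with a sensitivity analysis that counts their first PD. This also covers a late week-16 repeat scan that reaches the floor.

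Use the durable version as the clinical benefit outcome in Section 13.5. Keep the any-SD count beside it, labelled disease control rate, with the approximate no-effect reference and its assumptions.

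The cost is wording in Sections 13.4 and 13.5, with no added scans. The headline CBR will be lower and less comparable with trials that count any SD, which the retained rate offsets. Fewer benefit cases will also leave less information for the biomarker models: with no drug effect, 9-12% of 38 is 3-5 patients.

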### 13.5 Exploratory and Correlative Endpoints

- The study is not powered to detect specific hypotheses, rather this data and analysis will help better identify patients that have the potential to benefit from this therapy and aid in designing larger Phase III studies. No direct comparisons will be made between the single and dual agent regimens. We will address the issue of multiple comparisons at the time of the analyses, which will be dependent on the number of hypotheses investigated.
- To assess the potential association between PD-L1 expression (by IHC) and clinical outcome, within each study treatment arm. Categorical data analysis and logistic regression will be used to evaluate the associations between PD-L1 expression (by IHC) and clinical outcome (eg, response, clinical benefit, progression-free survival, and survival). Kaplan-Meier methodology and Cox Proportional Hazards models will be used to evaluate time to event endpoints.
- To evaluate the associations between selected biomarker measured in serial peripheral blood and with clinical efficacy, within each study component. Summary statistics will be used to for describing changes across time. In addition, the time course of biomarker outcomes will be investigated graphically, by summary plots or individual patient plots. Categorical data analysis and logistic regression will be used to evaluate the associations between PD-L1 expression (by IHC) and clinical outcome (eg, response, clinical benefit, time to progression, progression-free survival, and survival). If there is suggestion of meaningful trend, methods such as linear mixed models may be used to characterize the pattern of change over time. Kaplan-Meier methodology and Cox Proportional Hazards models will be used to evaluate time to event endpoints.
- To evaluate the association between selected biomarker measured in tumor tissue with clinical efficacy, within each study component. Categorical data analysis and logistic regression will be used to correlated biomarkers with and clinical outcome (eg, response, clinical benefit, time to progression, progression free survival, and survival) within each study component. Kaplan-Meier methodology and Cox Proportional Hazards models will be used to evaluate time to event endpoints.
- Confirmed response and secondary endpoints will be evaluated in patients who crossover from single agent nivolumab to dual agent treatment following progression. The date used for the calculations of duration of response, TTP, PFS, and OS will be the date the patient initiated crossover treatment with dual agent therapy.

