## 6.2 Specimen collection and submission

### 6.2.1 Overview of specimen collection and submission

For patients registered to substudy A091401-ST1: All participating institutions must ask patients for their consent to participate in the correlative substudy planned for Alliance A091401-ST1, although patient participation is optional. Serum studies, tumor and peripheral blood mononuclear cell (PBMC) genetic analysis and PBMC flow cytometry will be performed. Rationale and methods for the scientific components of these studies are described in [Section 14.0](#). For patients who consent to participate, tissue and blood will be collected at the following time points for these studies:

	Pre-treatment (not applicable to crossover to dual agent therapy)	Arm 1: Weeks 3,5,9, 11,13*	Arm 2: Weeks 4,7,10, 13,15*	Crossover to dual agent therapy Weeks 1,4,7,10,13 & 15	End of Cycle 1 (6 weeks): Includes crossover to dual agent therapy	End of Treatment	PD, withdrawal, or removal	Storage/ Shipping conditions	Submit to:
Mandatory for all patients pre-registered to A091401:									
Archival FFPE tumor block OR 1 representative H&E and 20 unstained tissue slides **	X(1)							See Section 6.2.3	OSU
For patients registered to A091401-ST1, submit the following:									
Fresh tumor biopsy	X(2)			X (3)	X			See Section 6.2.4	OSU
Peripheral whole blood (EDTA)***	1 x 10 mL							See Section 6.2.5	OSU
Peripheral whole blood (non-additive red top) Ω	1 x 10 mL	1 x 10 mL	1 x 10 mL	1 x 10 mL		1 x 10 mL	1 x 10 mL	See Section 6.2.5	OSU
Peripheral whole Blood (green top heparin) Ψ	2 x 10 mL	2 x 10 mL	2 x 10 mL	2 x 10 mL		2 x 10 mL	2 x 10 mL	See Section 6.2.5	OSU

\* Correlative time points for blood-should be drawn on the visit and day of treatment for each arm. See [Section 5.0](#) for dates of clinical assessments. All correlative time points have a window of  $\pm 1$  week. Correlates obtained outside these windows may be included in analysis after discussion with the Study Chair.

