### 6.2.5 Blood sample submission (A091401-ST1)

For patients who consent to A091401-ST1, whole blood samples will be used for the analyses described in [Section 14.1](#). From consenting patients:

- Collect 10 mL of venous blood in lavender top (EDTA anticoagulant) vacutainer tube(s) at baseline. The tubes should be inverted approximately 8-10 times to mix the EDTA. Refrigerate sample until shipping. The sample should be placed in a biohazard bag shipped according to IATA guidelines the same day as the blood is drawn on a cold pack by overnight courier service to the Alliance Biorepository at OSU for germline DNA extraction.
- Collect 10 mL of peripheral venous blood in red top vacutainer tube(s) at the following time points:
  - Arm 1: Baseline, Weeks 3,5,9, 11, 13; End of treatment; PD, withdrawal or removal from study.
  - Arm 2: Baseline, Weeks 4, 7, 10, 13, 15; End of Treatment; PD, withdrawal, or removal from study.
  - Crossover to dual agent therapy upon progression on Arm 1: Weeks 1, 4, 7, 10, 13, 15; End of Treatment; PD, withdrawal, or removal from study.

Gently invert approximately 5 times to mix clot activator with blood. Let blood clot for 30 minutes. Observe a dense clot. Refrigerate the sample until shipping. The sample should be placed in a biohazard bag and shipped according to IATA guidelines the same day as the blood is drawn on cold pack by overnight courier service to the Alliance Biorepository at OSU for serum preparation.

- Collect 2 x 10 mL of peripheral venous blood into green top (sodium heparin) vacutainer tubes at the following time points:
  - Arm 1: Baseline, Weeks 3, 5, 9, 11, 13; End of treatment; PD, withdrawal or removal from study.
  - Arm 2: Baseline, Weeks 4, 7, 10, 13, 15; End of Treatment; PD, withdrawal, or removal.
  - Crossover to dual agent therapy upon progression on Arm 1: Weeks 1, 4, 7, 10, 13, 15; End of Treatment; PD, withdrawal, or removal from study.

Invert tubes approximately 8-10 times to mix the sodium heparin solution. Specimens should be kept at room temperature until shipping. Samples should be placed in a biohazard bag and shipped according to IATA guidelines the same day as the blood is drawn and shipped at ambient temperature by overnight courier service to the Alliance Biorepository at OSU for PBMC isolation. Please do NOT use cold pack during shipping for the whole blood sodium heparin (green top) samples.

Label samples with the following identification:

- 1) Procurement date

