If the decision is made to continue treatment after progressive disease is identified within the initial 12 weeks (and criteria above are met), then the patient may continue therapy for a maximum of 4 weeks. **Note:** At this time, the baseline scan to use for further assessments of disease status is reset to this assessment. After 4 weeks a scan is to be repeated. If the scan shows progression compared to the scan 4 weeks prior, they should be removed from protocol therapy. If the scan shows stable disease or response, compared to the scan 4 weeks prior, they can remain on protocol therapy should they choose to and the suspected initial progression date and assessment is considered the baseline scan to use for until further PD is evident. See section [11.4.3.2](#) for more information for determining objective status and [section 12.1](#) for information regarding duration of therapy. Scan schedule will resume routine schedule, as per [Section 5.0](#) footnote D.

Patients who have progression AFTER the initial 12-week period will be removed from protocol therapy in arm 2 (arm 1 patients may elect to cross over to dual agent therapy with progression after a minimum of 10 weeks of single agent nivolumab).

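### Blood-marker time course (13.5): scheduled draws stop with treatment and the mixed model waits for a visible trend, so dropout can create or hide one

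*Combined protocol and SAP*

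**What the plan says.** The time-course plan for serial peripheral-blood markers is in section 13.5. It reads "Summary statistics will be used to for describing changes across time" and adds that the course will be looked at graphically, in summary plots or individual patient plots. The longitudinal model follows on a condition: "If there is suggestion of meaningful trend, methods such as linear mixed models may be used to characterize the pattern of change over time". The section does not say whether the summaries are visit means or changes from each patient's baseline. It names no analysis set and has no rule for patients who stop.

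The sampling rules are in section 6.2. The schedules in 6.2.5 are "Arm 1: Baseline, Weeks 3,5,9, 11, 13; End of treatment; PD, withdrawal or removal from study" and "Arm 2: Baseline, Weeks 4, 7, 10, 13, 15; End of Treatment; PD, withdrawal, or removal from study". Section 6.2.1 ties the draws to dosing: "Correlative time points for blood-should be drawn on the visit and day of treatment for each arm". A patient who stops treatment should therefore give an exit sample but no further scheduled ones. Section 13.5 does not say how exit samples enter the time course.

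Two other places bear on who is still being sampled. Section 1.1 gives historical PFS for previously treated patients: "PFS was 21% at 3 months for inactive drugs/regimens, and 39% for active drugs", and "6 month PFS was 8% with inactive regimens, and 14% for active regimens". Section 7.1 allows treatment past imaging progression in the first 12 weeks: if its criteria are met, "then the patient may continue therapy for a maximum of 4 weeks", and longer if the repeat scan shows no further progression.

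**The concern.** The group giving scheduled samples shrinks over the series, and it shrinks mainly through progression. If a marker's level is related to how long patients stay on treatment, the visit mean drifts as the group changes, even when every patient's own value is flat. The same drift can cancel a real within-patient change.

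The condition on the mixed model adds to this. The model uses each patient's repeated values and is less exposed to the problem, yet it is called on only if a trend is suggested first. Where the suggestion comes from an unpaired summary, dropout can prompt the model needlessly or leave a real change unmodelled.

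At stake are the descriptions of change under objectives 2.3.3, 14.1.2.2 and 14.1.2.3. Section 13.5 expects this work to help identify patients who may benefit and to help design larger trials.

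**Working it through.** The plan states no retention figure, sample size or power for this analysis, so there is no figure of its own to reproduce. The steps below show what size of distortion is plausible.

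**1. Share progression-free at the start of week 13 (12 elapsed weeks).** Inputs: 3-month PFS of 21% and 39% (section 1.1); 3 months = 13.04 weeks; constant hazard (assumption). S(t) = S(3 months)^(t/13.04).
- 0.21^(12/13.04) = 0.238
- 0.39^(12/13.04) = 0.421

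Fitting the constant hazard to the 6-month values instead gives 0.08^(12/26.09) = 0.313 and 0.14^(12/26.09) = 0.405, which lie inside that range. At 24-42%, the counts are about 9-16 of 38, 3-5 of 12 and 6-10 of 24 per arm, before refusals of the optional substudy.

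**2. Share on treatment if some continue past progression.** Let f be the fraction of patients with progression in the previous 4 weeks who are still treated (assumption). The share is S(12) + f × [S(8) − S(12)], with S(8) = 0.384 and 0.561.
- f = 0.25: 0.274 and 0.456
- f = 0.50: 0.311 and 0.491
- f = 1.00: 0.384 and 0.561

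So about 27-56% for f from 25% to 100%.

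**3. GIST.** Section 1.9 gives median time to progression of 6.4 weeks (placebo) and 27.3 weeks (sunitinib). With a constant hazard, 0.5^(12/6.4) = 0.27 and 0.5^(12/27.3) = 0.74.

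**4. Shift in an unpaired visit mean.** If retained patients differ at baseline by d from those who left, and p is the share retained, the mean of those retained differs from the full-group mean by d × (1 − p). For d = 0.5 SD (illustrative; no document supplies d):
- p = 0.24: 0.5 × 0.76 = 0.38 SD
- p = 0.42: 0.5 × 0.58 = 0.29 SD
- p = 0.56: 0.5 × 0.44 = 0.22 SD
- p = 0.74: 0.5 × 0.26 = 0.13 SD

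For d = 0 the shift is zero at any p. The masking case is the same sum reversed: a true within-patient fall of 0.29 SD would be cancelled by the shift at p = 0.42.

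**5. Comparison of methods.** A simulation gave every patient a flat marker, with 70% of variance between patients (assumption) and correlation rho between the patient's underlying level and time to dropout (assumption). It used the Arm 1 visit times, exponential dropout as in step 1, and 3,000 patients per scenario. The true change from baseline to 12 weeks is 0. Results in SD:

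| 3-month PFS | rho | Visit mean | Paired change | Random-intercept mixed model |
|---|---|---|---|---|
| 21% | 0 | +0.02 | 0.00 | −0.01 |
| 21% | 0.3 | +0.30 | +0.03 | +0.08 |
| 21% | 0.5 | +0.59 | −0.01 | +0.13 |
| 39% | 0 | −0.04 | −0.04 | −0.04 |
| 39% | 0.3 | +0.26 | +0.01 | +0.04 |
| 39% | 0.5 | +0.36 | −0.02 | +0.06 |

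The rho = 0 rows show simulation noise of up to about 0.04 SD. Paired change stays within that noise throughout, and the mixed model removes most of the artefact.

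**The case against.** The strongest reply is that 13.5 leaves the method open and does not describe a biased one. A reader might infer that it summarises each visit over whoever is still on treatment, but no such sentence exists; that reading comes from joining 13.5 to the sampling schedule. The section also lists individual patient plots, which show within-patient change directly. Sections 14.1.2.2 and 14.1.3.3 relate changes in circulating markers to clinical benefit, which presupposes a change for each patient. Nothing forbids fitting the mixed model without a visible trend. All of this stands, and it makes the point one of missing specification.

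A reader might also infer that week 13 contains only non-progressors. Section 7.1 rules that out. Footnote D to the study calendar places the repeat scan at week 10 or 16, so a patient progressing at the week-12 scan may still be treated and sampled at weeks 13 and 15. Progression is also found at scans, so attrition comes in steps.

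The 24-42% is historical PFS on other drugs, not retention in this trial. Treatment past progression raises the on-treatment share, and stopping for toxicity lowers it. GIST may behave quite differently. Exit samples mean that those who leave are not wholly unobserved, although they are tied to an event and not to a scheduled week.

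These replies limit the size of the problem. They do not supply an analysis set, a paired-change rule, a use for the exit samples, or a reason to make the model wait for a trend.

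**Conclusion.** The point holds as a minor gap in an exploratory analysis. Scheduled sampling follows treatment, 13.5 does not say how dropout is handled, and its one model-based method is optional and conditional on a display that dropout can distort in either direction.

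The size is illustrative: about 0.13-0.38 SD in a week-13 visit mean for a 0.5 SD baseline difference, over retained shares of 24-74%. This rests on historical progression figures, a constant hazard, an assumed rate of treatment past progression, an assumed baseline difference, and an unpaired summary.

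The tempting stronger statement is that attrition alone produces a trend. The documents do not support it. The marker must be related to time to dropout and the summary must be unpaired; without either, the shift is zero. No primary or secondary conclusion depends on this analysis.

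**What to change.** In section 13.5:

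- Summarise change from each patient's own baseline at each visit, with the number of pairs. State that a late-visit change describes the patients sampled then.
- Fit the linear mixed model to all available samples, however the plots look. Include end-of-treatment and progression samples at their actual dates.
- Where numbers allow, show profiles by time of dropout as a descriptive sensitivity display. A formal dropout-group factor would be too sparse in the 12-patient arms, where about 3-5 patients may remain at week 13.
- Before defining visits, reconcile the schedules. Section 6.2.5 lists Arm 2 weeks 13 and 15, while sections 14.1.3.2 and 14.1.3.3 list weeks 14 and 16 and add week 1 in both arms.

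The cost is SAP wording and a little programming, with no new samples or visits. Intervals at late visits will be wider, and the smallest arms will support little beyond description.
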